overall and stratified by clinical setting. For these analyses the order will be used as the unit of analysis (rather than the order session), because a provider may open or close patient records while placing a series of orders during a single order session. We will report the number of RAR events per 100,000 orders along with 95% binomial confidence intervals, as well as the percentage of all orders placed under those conditions. These results will be presented for the unrestricted arm overall, and disaggregated by clinical location.

**Sample Size**. For pragmatic reasons, sample size is not determined by the investigators but will represent the data that is available during the study period. Moreover, as noted, orders do not represent independent events, but are clustered within order sessions that, in turn, are clustered within providers. The magnitude of the effects at these levels are not currently known. Based on prior experience in this setting, in 1 year of data collection we expected to obtain approximately 9,000,000 orders in 2,400,000 order sessions, placed by 3,200 distinct providers for 440,000 distinct patients. We assumed 100 wrong-patient order sessions per 100,000 order sessions in the Unrestricted arm, and an intra-provider correlation of 0.01. With accrual of approximately 1,600 providers in each randomization arm, and a trial duration yielding an average of approximately 1,300 order sessions per provider with a coefficient of variation of 1.2, the trial would have >99% power to detect an odds ratio of 0.5 (or lower), 96% power to detect an odds ratio of 0.7.

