**Missing Data.** Due to the automatic functioning of the electronic health record, we do not anticipate that there will be missing data concerning RAR events, the system configuration of restricted mode vs. unrestricted mode, the number of records open at the time of placing an order, or provider-level covariates. There may be sporadic missing information regarding the patient-level covariates. In preliminary data, in a data set of more than 11.6 million orders, there were no missing observations for patient age, sex, or race. An indicator for Hispanic ethnicity was missing in just 4 records. With similar levels of missing data, we feel comfortable that restricting regression models to only include cases with complete data will not introduce appreciable levels of bias. If we find that any variables are missing for more than 1 record per 1,000 (after backfilling based on other records involving the same patient), we will extend our analyses to address this. We will presume that data are missing at random and will apply multiple imputation with chained equations.

**Interim Analysis.** To safeguard against the possibility that our intervention actually worsens (increases) the rate of RAR events, and to prevent unnecessary continuation of a study that is already conclusive, we will have a data safety monitoring committee conduct one interim review of the data in the randomized trial. After 6 months, we expect 50% of the data to have been accrued. Using the Lan-Demets alpha spending procedure with symmetric O'Brien-Fleming boundaries, the stopping rule at the interim review will be a z-statistic of magnitude 3.0318 or greater. The associated nominal p-value is 0.0024. Combined with a final analysis using a critical z-value of 1.9669 (nominal P=0.0492), we will have spent our overall alpha of 0.05 at the end of the study. The effects of this interim analysis procedure on nominal statistical power (see above) is negligible, less than 0.5 percentage points, so no adjustments to data collection need be made to account for this.

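### Power assumes about 1,300 order sessions per provider, but the plan's own one-year volumes give 750, and no stated study period reconciles them

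*Combined protocol and SAP*

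**What the plan says.** All of this is in the Final Statistical Analysis Plan.

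- **Sample Size** sets no target: "sample size is not determined by the investigators but will represent the data that is available during the study period".
- It then gives the expected yield: "in 1 year of data collection we expected to obtain approximately 9,000,000 orders in 2,400,000 order sessions, placed by 3,200 distinct providers".
- The power calculation follows: "With accrual of approximately 1,600 providers in each randomization arm", combined with "a trial duration yielding an average of approximately 1,300 order sessions per provider". The other inputs are a coefficient of variation (CV) of 1.2 for sessions per provider, 100 wrong-patient sessions per 100,000 in the unrestricted arm, and an intra-provider correlation of 0.01. The stated result is more than 99% power at an odds ratio (OR) of 0.5 and 96% at 0.7.
- **Interim Analysis** fixes the timing of the single look: "After 6 months, we expect 50% of the data to have been accrued". It then refers back to the power figure: "The effects of this interim analysis procedure on nominal statistical power (see above) is negligible, less than 0.5 percentage points".

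The text available gives neither a length nor dates for the study period. Protection of Human Subjects in the protocol schedules data extraction at the midpoint and the end, but dates neither.

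**The concern.** The yearly volumes and the power inputs use the same number of providers, 3,200 in total, yet they imply very different session counts per provider. The gap is too large to be rounding. A trial longer than one year could close it, but none is stated, and the interim timing points to 12 months.

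This matters because the sample is whatever accrues during the study period. Duration is therefore the only quantity that fixes how much data the trial was meant to have. The two paragraphs from which a reader could infer it disagree. The interim paragraph relies on the power figure to conclude that data collection needs no adjustment, so both paragraphs are meant to describe one trial.

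**Working it through.** **Inputs.** Sample Size gives 2,400,000 sessions and 9,000,000 orders in one year, 3,200 providers (1,600 per arm), 1,300 sessions per provider, CV 1.2, control rate 0.001 and correlation 0.01. Interim Analysis gives 50% of the data at 6 months, with critical values 3.0318 (interim) and 1.9669 (final). Primary Analysis gives a two-sided 0.05 Wald test in a random-intercept logistic model.

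**Volumes.**

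- Sessions per provider in one year: 2,400,000 / 3,200 = 750. The power input is 1,300 / 750 = 1.73 times this.
- Sessions needed for 1,300 each: 3,200 × 1,300 = 4,160,000. At 9,000,000 / 2,400,000 = 3.75 orders per session, that is 15.6 million orders rather than 9.0 million.
- Time needed at the stated volume: 4,160,000 / 2,400,000 = 1.733 years = 20.8 months. Six months would then hold 6 / 20.8 = 28.8% of sessions, not 50%.
- Providers that one year could supply at 1,300 each: 2,400,000 / 1,300 = 1,846, not 3,200.

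The durations assume constant accrual and a fixed set of providers.

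**Power at m = 1,300 and m = 750.** The SAP names no method, so several were tried, all two-sided at 1.96 with 1,600 providers per arm.

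1. *Design effect with the CV*, 1 + ((1.2² + 1)m − 1) × 0.01. At m = 1,300 this is 32.71, so 1,600 × 1,300 / 32.71 = 63,589 effective sessions per arm. At m = 750 it is 19.29, giving 62,208.
2. *Design effect without the CV*, 1 + (m − 1) × 0.01. This is 13.99 and 8.49, giving 148,678 and 141,343 effective sessions.
3. *Inverse-variance weighting of providers*, with gamma or lognormal session counts at CV 1.2.
4. *Random-intercept logistic model*, using expected Fisher information. Assumptions not in the SAP: the 0.01 is on the proportion scale, provider effects are normal on the logit scale (intercept −8.175, SD 1.600), and counts are gamma or lognormal. The standard errors of the log OR are 0.0906 / 0.0865 at 1,300 and 0.1008 / 0.0965 at 750 (gamma / lognormal). For example, |ln 0.7| / 0.1008 − 1.96 = 1.58, which gives 94.3%.

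| Method, OR 0.7 (stated 96%) | m = 1,300 | m = 750 |
|---|---|---|
| Design effect with CV | 45.0% | 44.2% |
| Design effect without CV | 80.1% | 78.1% |
| Inverse-variance, gamma | 72.8% | 68.9% |
| Inverse-variance, lognormal | 77.1% | 73.6% |
| Random intercept, gamma | 97.6% | 94.3% |
| Random intercept, lognormal | 98.5% | 95.9% |

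If the 0.01 is instead on the latent logistic scale, power exceeds 99.9% at both values. None of these methods gives 96% at m = 1,300. One comes within rounding of it at 750, but that does not show which input was used.

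At OR 0.5 (stated above 99%), the random-intercept model gives over 99.9% at both values. The design effect with the CV gives 90.2% and 89.6%.

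**Type I error.** Statistical information does not grow in proportion to sessions. Under method 4 at OR 0.7, information on the arm effect (gamma / lognormal) is 71.8 / 77.5 at 375 sessions per provider (6 months), 98.4 / 107.4 at 750, and 121.7 / 133.6 at 1,300. The 6-month information fraction is therefore 0.73 / 0.72 if the total is 750, and 0.59 / 0.58 if it is 1,300. With the stated boundaries and correlation √t between the two looks, overall type I error is 0.0499 at t = 0.50, 0.0497 at 0.58 to 0.59, and 0.0493 to 0.0494 at 0.72 to 0.73.

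**The case against.** The strongest reply is that little depends on this number. The power statement sizes nothing, because the sample is whatever accrues. Under a random-intercept model, which is the planned primary analysis, 750 sessions per provider still gives 94% to 96% power at OR 0.7 and over 99.9% at OR 0.5, close to what is stated. All of that stands, and it limits the point to a planning input that needs correcting.

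A second reply is that the power sentence refers only to some duration, which may exceed one year. The documents never say so. The interim timing implies about 12 months, and extraction at the midpoint and the end is consistent with a 6-month midpoint. New hires are also randomized during the trial, so a longer trial would probably add providers and make 1,300 each harder to reach. The same fact makes the 20.8 months and 28.8% illustrative rather than exact. Front pages were removed from the text reviewed, so dates may appear there. Even so, no single period would make both paragraphs right at the stated volumes.

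A third reply is that 750 may not be right either. Preliminary Studies reports 1,388 providers with retracted and reordered orders, and says about 1 in 6 providers erred. If those 1,388 are the numerator, there were about 1,388 × 6 = 8,328 ordering providers, not 3,200. This does not support 1,300, but it is a reason to confirm the volumes before substituting 750.

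**Conclusion.** The concern holds. The power input of 1,300 sessions per provider contradicts the 750 implied by the same paragraph, by a factor of 1.73, and it contradicts the 6-month, 50% interim statement. The simplest reading is a 12-month plan with one input that does not match it, but the text does not settle this.

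The consequence for power is small. At OR 0.7, moving from 1,300 to 750 costs under 1 to about 4 points across the methods tried with the correlation on the proportion scale. The stated boundaries do not inflate type I error. The choice of method matters far more: at 1,300 sessions, power at OR 0.7 runs from 45.0% to 98.5% under proportion-scale readings of the correlation. This check therefore gives no view on whether the trial is adequately powered.

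The volume arithmetic rests only on the SAP's own figures. The random-intercept results rest on the assumptions listed with them.

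**What to change.** State the study period in the SAP, as a length or as start and end dates, and make Sample Size and Interim Analysis agree with it.

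- **If it is 12 months:** confirm the 2,400,000 sessions and 3,200 providers, replace 1,300 with 750, rerun the power calculation and restate the result.
- **If it is longer:** state the duration, show how it yields 1,300 sessions per provider, and correct the 6-month, 50% statement.

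In either case, name the power method, the scale of the 0.01 correlation and the assumed distribution of session counts. The restated power should come from the sponsor's own rerun, not from the figures here.

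The cost is SAP wording and one rerun. The stated power may fall by a few points from the input alone, and possibly by more once the method is named. The primary model, stopping boundaries and enrolment stay as they are.

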**Primary Analysis (Aim 1)**. The primary analysis of the randomized trial is intention-to-treat, with each provider generating a cluster of order sessions. Hence, the order session will be used as the unit of analysis. The primary outcome variable is dichotomous, indicating whether or not each order session contains a wrong-patient RAR event. To determine the effect of trial arm on wrong-patient orders, we will construct a random effects logistic regression model with wrong-patient order sessions as the outcome, and randomization arm as the independent variable, using provider as a random intercept to account for clusters of order sessions within providers. We will estimate the effect of the restricted mode versus the unrestricted mode on the rate of RAR events using the odds ratio and its 95% confidence interval (CI), and will test the null hypothesis using the Wald test with a two-tailed significance level of 0.05. The primary outcome is reported as the number of wrong-patient order sessions per 100,000 order sessions.

**Subgroup Analysis (Aim 2).** Additional analyses of the effect of the restricted mode versus the unrestricted mode in specified clinical locations will be carried out by including indicators for the locations and location-study arm interaction terms in the model. For subgroup analyses, we will compare the rate of RAR events in emergency department, outpatient, and inpatient settings, and more specifically in inpatient units, including medical/surgical, critical care, pediatrics, and obstetrics units. We will construct similar mixed-effects logistic regression models for each predefined subgroup, with a separate model including an interaction term to test the significance of treatment effects across subgroups, using the Wald test for significance.

**As-Treated Analysis**. Because of administrative errors, some providers were not assigned to the trial arm to which they were randomized. Therefore, we will repeat all assessments in as-treated analyses (ie, according to treatment received) such that each order or order session was characterized by the provider's configuration at the time the orders were placed.

For orders placed in the unrestricted mode, we will examine the rate of RAR events and the percentage of orders placed when one, two, three, or four records were open at the time of ordering,

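### The printed interim and final critical values (3.0318 and 1.9669) belong to a look at 48% information, not the stated 50%, and the primary analysis does not point to the adjusted final level

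*Combined protocol and SAP*

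**What the plan says.** In the SAP's Interim Analysis section, a monitoring committee is to "conduct one interim review of the data in the randomized trial". On timing: "After 6 months, we expect 50% of the data to have been accrued". The boundaries are set "Using the Lan-Demets alpha spending procedure with symmetric O'Brien-Fleming boundaries", and "the stopping rule at the interim review will be a z-statistic of magnitude 3.0318 or greater", with nominal p 0.0024. The last step is a "final analysis using a critical z-value of 1.9669 (nominal P=0.0492"), after which "we will have spent our overall alpha of 0.05 at the end of the study". The bounds are given as fixed numbers, with no provision to recompute them at the fraction actually observed.

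The Primary Analysis (Aim 1) section says of the main comparison that the investigators "will test the null hypothesis using the Wald test with a two-tailed significance level of 0.05". It does not refer to the interim section or to 0.0492.

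**The concern.** Number of looks, timing, spending function and overall alpha are all stated, so the two critical values are fully determined and a reader should be able to reproduce them. They cannot be reproduced at 50%. The committee would apply a fixed interim value that does not follow from the timing stated just before it.

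The second point is one of wording. An analyst working from the Primary Analysis section alone would compare the final Wald statistic with 1.960, and one working from the Interim Analysis section would use 1.9669. Taken literally, the two sections decide a final p-value between 0.0492 and 0.05 differently.

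**Working it through.** **Inputs.** Overall two-sided alpha is 0.05 (Primary Analysis and Interim Analysis). There are two analyses, with the interim at t = 0.50, and Lan-DeMets O'Brien-Fleming-type spending with symmetric bounds (Interim Analysis).

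**Method.** Each tail spends 0.025. Up to fraction t the spend per tail is 2 × [1 − Φ(z₀.₉₈₇₅/√t)], with z₀.₉₈₇₅ = 2.2414. The interim bound c₁ is the normal quantile that leaves this amount in each tail. The final bound c₂ solves P(|Z₁| < c₁, |Z₂| < c₂) = 0.95 with corr(Z₁, Z₂) = √t, by numerical integration.

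**The plan's p-values.** |z| = 3.0318 gives p = 0.00243 and |z| = 1.9669 gives p = 0.04919. The printed p-values match the printed z-values.

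**At the stated 50%.** 2.2414/√0.50 = 3.170, so the two-sided spend is 4 × [1 − Φ(3.170)] = 0.00305.

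**At 48%.** 2.2414/√0.48 = 3.235, so the two-sided spend is 4 × [1 − Φ(3.235)] = 0.00243.

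| | Interim z (p) | Final z (p) |
|---|---|---|
| Printed in the SAP | 3.0318 (0.0024) | 1.9669 (0.0492) |
| Named method, t = 0.50 | 2.9626 (0.0031) | 1.9686 (0.0490) |
| Named method, t = 0.48 | 3.0318 (0.0024) | 1.9669 (0.0492) |
| Whole 0.05 spent through one function, t = 0.50 | 2.7718 (0.0056) | 1.9793 (0.0478) |
| Classical O'Brien-Fleming, t = 0.50 | 2.7965 | 1.9774 |

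Solving c₁ = 3.0318 for the fraction gives t = 0.47999, and the matching final bound is 1.96688. Both printed values therefore point to 0.48, and neither alternative convention at 50% reproduces them.

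**Overall type I error of the printed pair, by true information fraction** (0.40 to 0.70 is an assumed range):

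| t | 0.40 | 0.45 | 0.48 | 0.50 | 0.60 | 0.70 |
|---|---|---|---|---|---|---|
| alpha | 0.0503 | 0.0501 | 0.0500 | 0.0499 | 0.0496 | 0.0494 |

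**If the final test used 1.960.** With an interim bound of 3.0318 at t = 0.50, overall alpha is 0.0507. With 2.9626 it is 0.0510.

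**Power.** Take the SAP's 96% (odds ratio 0.7) as given. The drift is 1.960 + 1.751 = 3.711, so the interim statistic has mean 3.711 × √0.50 = 2.624.

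- Chance of crossing at the interim: 1 − Φ(3.0318 − 2.624) = 1 − Φ(0.408) = 34.2% with the printed bound, and 1 − Φ(2.9626 − 2.624) = 1 − Φ(0.339) = 36.7% with the 50% bound. By symmetry the same holds for an effect of equal size in the harmful direction.
- Overall power: 95.96% with the printed pair and 95.95% with the 50% pair. The loss from 96% is 0.04 to 0.05 points, so the SAP's statement of less than 0.5 points holds.

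**The case against.** The case against rests on three arguments.

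First, 50% is only a forecast for a six-month look, and a spending function does not require the look to fall exactly there. The authors may have run the method correctly at 48% and rounded the figure in the text. That is possible, and it makes this an unstated fraction rather than a faulty calculation. It does not remove the mismatch, because the bounds are fixed numbers and nothing says they will be recomputed.

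Second, no error-rate or power claim fails at 50%: alpha is just under 0.05 and the interim bound errs on the strict side. This stands, and it is why the point is minor. One qualification is that alpha would marginally exceed 0.05 if the true fraction fell below 0.48, reaching 0.0503 at 0.40.

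Third, giving overall alpha in the primary analysis and the adjusted level in the interim section is ordinary drafting, and the explicit critical value should govern. This largely stands. The Interim Analysis section itself calls 0.05 the overall alpha, so the Primary Analysis section can be read the same way. The adjustment is in the plan and only the cross-reference is missing. On its own this would be a missing detail, not an error.

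**Conclusion.** The concern holds, and it is minor. The two decision thresholds do not follow from the plan's stated inputs: they are the values for 48% information, while the text says 50%. The primary analysis gives 0.05 without saying that this is the overall alpha.

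Only results very near a boundary would be decided differently:

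- interim |z| from 2.9626 to 3.0318;
- final |z| from 1.9669 to 1.9686;
- final |z| from 1.960 to 1.9669, if the Primary Analysis section is read literally.

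The largest practical effect is about 2.6 percentage points in the chance of stopping at the interim (36.74% − 34.16%), under an effect giving 96% nominal power. The boundary arithmetic uses only the plan's own inputs and the standard per-tail form of the spending function. The stopping and power figures also take the SAP's 96% as given.

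**What to change.** In the Interim Analysis section, either give 2.9626 (p 0.0031) and 1.9686 (p 0.0490) for a 50% look, or keep the printed pair and state that it is for 48%. Preferably, also say that both bounds will be computed from the spending function at the observed information fraction, taken as 1/SE² of the log odds ratio at the interim over its projected final value. The share of sessions accrued need not equal the share of information when sessions are clustered within providers. How far the two differ cannot be settled from the plan: it does not give the scale of the 0.01 correlation, and of the clustering effects the Sample Size section says "The magnitude of the effects at these levels are not currently known".

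In the Primary Analysis section, add a clause saying that 0.05 is the overall two-sided alpha and that the final Wald test uses the critical value from the Interim Analysis section.

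The cost is one rerun of the boundary calculation and two wording changes. Moving to the 50% pair makes the final critical value slightly stricter (1.9686 against 1.9669), and overall power falls by about 0.01 percentage points in the 96% scenario.
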